## 17.5 APPENDIX E: ROCKWOOD FRAILTY INDEX

Reference: Rockwood, K, et al. (47)

### Clinical Frailty Scale\*

**1 Very Fit** – People who are robust, active, energetic and motivated. These people commonly exercise regularly. They are among the fittest for their age.

**2 Well** – People who have **no active disease symptoms** but are less fit than category 1. Often, they exercise or are very **active occasionally**, e.g. seasonally.

**3 Managing Well** – People whose **medical problems are well controlled**, but are **not regularly active** beyond routine walking.

**4 Vulnerable** – While **not dependent** on others for daily help, often **symptoms limit activities**. A common complaint is being "slowed up", and/or being tired during the day.

**5 Mildly Frail** – These people often have **more evident slowing**, and need help in **high order IADLs** (finances, transportation, heavy housework, medications). Typically, mild frailty progressively impairs shopping and walking outside alone, meal preparation and housework.

**6 Moderately Frail** – People need help with **all outside activities** and with **keeping house**. Inside, they often have problems with stairs and need **help with bathing** and might need minimal assistance (cuing, standby) with dressing.

**7 Severely Frail – Completely dependent for personal care**, from whatever cause (physical or cognitive). Even so, they seem stable and not at high risk of dying (within ~ 6 months).

**8 Very Severely Frail** – Completely dependent, approaching the end of life. Typically, they could not recover even from a minor illness.

**9. Terminally III** - Approaching the end of life. This category applies to people with a **life expectancy <6 months**, who are **not otherwise evidently frail**.

#### Scoring frailty in people with dementia

The degree of frailty corresponds to the degree of dementia. Common symptoms in mild dementia include forgetting the details of a recent event, though still remembering the event itself, repeating the same question/story and social withdrawal.

In moderate dementia, recent memory is very impaired, even though they seemingly can remember their past life events well. They can do personal care with prompting.

In severe dementia, they cannot do personal care without help.

- 1. Canadian Study on Health & Aging, Revised 2008.
- 2. K Rockwood et al. A global clinical measure of fitness and frailty in elderly people. CMAJ 2005; 173:489-495.

© 2007-2009. Version 1.2. All rights reserved. Geriatric Medicine Research, Dalhousie University, Halifax, Canada. Permission granted to copy for research and educational purposes only.

## 17.6 APPENDIX F: MDS-SPECIFIC COMORBIDITY INDEX (MDS-CI)

Comorbidity	Definition	Variable Weighted Score (to be considered if the specific comorbidity is present)
Cardiac disease	Arrhythmia* Heart valve disease** Coronary artery disease*** or myocardial infarction Congestive heart failure or ejection fraction $\leq 50\%$	2
Moderate-to-severe hepatic disease****	Cirrhosis, fibrosis, persistent bilirubin $> 1.5 \times \text{ULN}$ or AST/ALT $> 2.5 \times \text{ULN}$	1
Severe pulmonary disease	DLCO and/or FEV1 $\leq 65\%$ or dyspnea at rest or requires oxygen	1
Renal disease	Persistent creatinine $> 2 \text{ mg/dL}$ , renal dialysis, or renal transplant	1
Solid tumor	Malignancy at any time point in the patient's history, excluding non-melanoma skin cancer	1

DLCO indicates diffusion capacity of the lung for carbon monoxide; FEV1: forced expiratory volume in one second; ULN: upper limit of normal; AST: aspartate aminotransferase; ALT: alanine aminotransferase. \*Atrial fibrillation or flutter, sick sinus syndrome, or ventricular arrhythmias; \*\*Except mitral valve prolapse; \*\*\*One or more vessel-coronary artery stenosis requiring medical treatment, stent, or bypass graft; \*\*\*\*HCV infection was documented in 7% of patients.

### MDS – CI Key

MDS-CI Risk	Sum of Individual Variable Scores
Low risk	0
Intermediate risk	1-2
High risk	$> 2$

 doi:10.3324/haematol.2010.033506

**17.7 APPENDIX G: EUROPEAN ORGANIZATION FOR RESEARCH AND TREATMENT OF CANCER (EORTC) QUALITY OF LIFE QUESTIONNAIRE = EORTC QLQC30 SCORE**

Reference: Fayers, P, et al.([50](#))

See Study Instrument Packet.

**17.8 APPENDIX H: PATIENT-REPORTED OUTCOMES (NIH ADULT PSYCHOSOCIAL ASSESSMENT FOR MDS, CTCAE, OVERALL SIDE EFFECT BOTHER, PROMIS PHYSICAL FUNCTION, PGI-S, AND PGI-C)**

See Study Instrument Packet.

## 17.9 APPENDIX I: DATA ELEMENTS TO CONSIDER FOR CRF ENTRY IN CLINICAL DATABASE

### Participant characteristics at protocol entry

- Sex (male, female)
- Age at enrollment (number)
- Ethnicity (white, black, American Indian/Alaskan native, Asian/Pacific islander, Hispanic, other)
- ECOG and Karnofsky performance status
- Diagnosis - MDS (high risk and higher intermediate risk)
- 2016 WHO classification of MDS (MDS with single lineage dysplasia [MDS-SLD], MDS with ring sideroblasts and single lineage dysplasia [MDS-RS-SLD], MDS with ring sideroblasts and multilineage dysplasia [MDS-RS-MLD], MDS with multilineage dysplasia [MDS-MLD], MDS with excess blasts [MDS-EB], MDS with isolated del(5q), MDS unclassifiable [MDS-U],
- Date of MDS diagnosis (month, year)
- Age at MDS diagnosis
- Revised International Prognostic Scoring System (IPSS-R) score at MDS diagnosis
- Cytogenetic profile at diagnosis and enrollment, if available (see Appendix C)- only need overall score (very good, good, intermediate, poor, very poor)
- Bone marrow blasts %, if available (flow/asp and IHC/bx)
- Hemoglobin, if available (at diagnosis and at enrolment) use counts from day of bone marrow for enrollment
- Platelet count, if available (at diagnosis and at enrolment) day of bone marrow for enrollment
- Absolute neutrophil count (ANC), if available (at diagnosis and at enrolment) day of bone marrow for enrollment
- RBC transfusion dependence (transfusion dependent or independent)
- Platelet transfusion dependence (transfusion dependent or independent)
- Average # of transfusions per month (RBCs units and instances of platelets transfusions) in the 3 months leading up to baseline on study
- Laboratory values will be collected from time of screening for duration of trial
- TP53 mutation status at enrollment, if available (TP53 mutation positive or negative)
- Names and # of cycles of prior Lines of therapy for MDS.
- Response to most recent line of therapy: CR (complete response), PR (partial response), HI (hematologic improvement), mCR with HI (marrow CR with hematologic improvement), mCR without HI (marrow CR without hematologic improvement), SD (stable disease), PD (disease progression)
- MDS-CI (low risk, intermediate risk, high risk)
- Rockwood frailty index (see Clinical Frailty Scale)
- Disease status at time of enrollment: CR (complete response), PR (partial response), HI (hematologic improvement), mCR with HI (marrow CR with hematologic improvement), mCR without HI (marrow CR without hematologic improvement), SD (stable disease), PD (disease progression)
- History of prior allogeneic transplantation (yes/no)
  - If history of prior allogeneic transplantation:

- Date of allogeneic transplant/Day 0
- Patient Reported Outcome Questionnaires (per section 3.5.3)

#### Data collection during study/treatment

- Cycle number & day of treatment
- Study Drug Administration
- Disease response at assessment timepoints: CR (complete response), PR (partial response), HI (hematologic improvement), mCR with HI (marrow CR with hematologic improvement), mCR without HI (marrow CR without hematologic improvement), SD (stable disease), PD (disease progression)
- Best overall response to study treatment: CR (complete response), PR (partial response), HI (hematologic improvement), mCR with HI (marrow CR with hematologic improvement), mCR without HI (marrow CR without hematologic improvement), SD (stable disease), PD (disease progression)
- Bone marrow percent blasts
- RBC transfusion dependence (transfusion dependent or transfusion independent)
- Platelet transfusion dependence (transfusion dependent or transfusion independent)
- # of transfusions per month (RBCs units and instances of platelets transfusions)
- Adverse events
- Patient Reported Outcome Questionnaires: (per section 3.5.3)

#### Data collection at post-therapy follow-up visits

- Alive (yes/no)
- Adverse events
- Progression of MDS (if yes, to what and when)
- Diagnosed with sAML (yes/no)
  - If diagnosed with sAML, date of sAML diagnosis (month, year)

#### Data collection at time of death

- Date of death
- Disease status at time of death: CR or not CR
- Cause of death: disease progression/relapse vs non-relapse mortality (definition of non-relapse mortality: subject in clinical remission at time of death)
- If non-relapse mortality, primary cause of death (per CTCAE)

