#### **1.1.3 Exploratory Objectives**

- To evaluate the relationship between KPT-8602 exposure (PK) and response
- To evaluate changes in XPO1 mRNA expression and other potential PD markers with treatment
- To assess changes in DNA damage repair by evaluation of gammaH2AX levels
- To evaluate compliance and feasibility of administering PRO in this patient population
- To evaluate tolerability of treatment by assess symptomatic adverse events, physical function and side effect bother
- To longitudinally describe and evaluate disease and treatment-related severity and functional well-being

- To determine meaningful change in disease and treatment-related symptoms and functional well-being by using anchors
- To evaluate changes in DNA methylation status pre- and post-treatment
- To evaluate changes in cell composition in the bone marrow and peripheral blood microenvironment pre- and post-treatment
- To evaluate changes in genetic clonal diversity during treatment
- To evaluate changes in gene expression patterns of tumor suppressor genes and oncogenes (including DNMT3B expression)
- To evaluate the influence of splicing factor mutations (U2AF1, SRSF2, SF3B1, ZRSR2) on nuclear shuttling
- To evaluate the degree of disruption of ribosome biogenesis after XPO1 inhibition
- To evaluate changes in nuclear and cytoplasmic protein composition using mass spectrometry
- To evaluate additional clinical outcomes, such as overall improvement rate (OIR), transfusion-independence (TI), cytogenetic response rate, time to best response (CR, PR, marrow CR + HI, HI), disease-free survival (DFS; definition: time to relapse for participants who achieve CR), progression-free survival (PFS; definition: time to progression or death from MDS), leukemia-free survival (LFS; definition: time to progression to AML or death from any cause), and overall survival (OS; definition: time to death from any cause)

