## 1.2 BACKGROUND AND RATIONALE

### 1.2.1 Myelodysplastic syndromes

The myelodysplastic syndromes (MDS) are a group of heterogenous clonal neoplasms of hematopoietic stem cells, characterized by dysplastic changes in at least one myeloid lineage, recurrent genetic aberrations, presence of up to 20% myeloblasts in the bone marrow, and high risk of evolution to acute myelogenous leukemia (AML). Myelodysplasia results in ineffective hematopoiesis with consequential peripheral blood cytopenia(s). Anemia is the most common clinical presentation of MDS, but other cytopenias are also often present. Cytopenias, together with ineffective maturation of neutrophils and platelets, often result in severe and/or recurrent infections and/or bleeding episodes, respectively. In general, it is estimated that up to 1/3 of patients with MDS will die from cytopenia-related complications, up to 1/3 have disease progression into a secondary AML with poor prognosis, and the remaining 1/3 may die from causes unrelated to their MDS.

MDS is a disease of the elderly, with a median age at diagnosis of approximately 75 years, with ~80% of patients being  $\geq 65$  years. Based on cancer registry data, about 10,000 new MDS cases are diagnosed per year in the United States, but the number is probably underestimated, and may be as high as >40,000 based on Medicare claims analyses. There is a slight predominance of males.

Most MDS patients (~90%) have sporadic disease and the remainder are therapy-related MDS (t-MDS), the latter often presenting in patients younger than 60 years of age. In the last decade,

familial related myeloid neoplasia in persons with germ-line mutations (i.e., *RUNX1*, *GATA2*, *DDX41*, *CEPBA*, *ANKRD26*, *ETV6*) is recognized as a predisposing condition for earlier acquisition of additional MDS-related mutations and MDS development.[\(9\)](#) Additionally, MDS can also develop from the rare inherited bone marrow failure disorders, such as Fanconi and Diamond-Blackfan anemia, which can present in childhood and adolescence.[\(10\)](#)

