Disease progression	
For participants with:
 
 
• Less than 5% blasts: <math>\geq 50\%</math> increase in blasts to <math>> 5\%</math> blasts
 
• 5%-10% blasts: <math>\geq 50\%</math> increase to 10% blasts
 
• 10%-20% blasts: <math>\geq 50\%</math> increase to <math>> 20\%</math> blasts
 
• 20%-30% blasts: <math>\geq 50\%</math> increase to <math>> 30\%</math> blasts
 
 
Any of the following:
 
 
• At least 50% decrement from maximum remission/response in granulocytes or platelets
 
• Reduction in Hgb by <math>\geq 2</math> g/dL
 
• Transfusion dependence
 

Survival	
Endpoints:
 
 
• Overall: death from any cause
 
• Event free: failure or death from any cause
 
• PFS: disease progression or death from MDS
 
• DFS: time to relapse
 
• Cause-specific death: death related to MDS
 

MDS, myelodysplastic syndromes; Hgb, hemoglobin; CR, complete remission; HI, hematologic improvement; PR, partial remission; FAB, French-American-British; AML, acute myeloid leukemia; PFS, progression-free survival; DFS, disease-free

survival.

To convert hemoglobin from grams per deciliter to grams per liter, multiply grams per deciliter by 10.

\*Dysplastic changes should consider the normal range of dysplastic changes.

†In some circumstances, protocol therapy may require the initiation of further treatment (eg, consolidation, maintenance) before the 4-week period. Such participants can be included in the response category into which they fit at the time the therapy is started. Transient cytopenias during repeated chemotherapy courses should not be considered as interrupting durability of response, as long as they recover to the improved counts of the previous course.

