### **8.4 WAIVER OF EXPEDITED REPORTING TO CCR**

As death due to disease progression is part of the study objectives (PFS), and captured as an endpoint in this study, they will not be reported in expedited manner to the sponsor. However, if there is evidence suggesting a causal relationship between the study drug and the event, the event will be reported in an expedited manner according to Section **8.3**.

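### The cause-of-death field in Appendix I follows remission status, so it cannot identify the deaths from MDS that PFS and cause-specific death require

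*Combined protocol and SAP*

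**What the plan says.** The list of data to collect at death in Appendix I has three linked elements:

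- disease status: "Disease status at time of death: CR or not CR";
- cause: "Cause of death: disease progression/relapse vs non-relapse mortality (definition of non-relapse mortality: subject in clinical remission at time of death");
- a follow-on item, asked conditionally: "If non-relapse mortality, primary cause of death (per CTCAE").

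Two endpoints depend on why the participant died. Section 1.1.3 gives "progression-free survival (PFS; definition: time to progression or death from MDS"), and the response-criteria table in 6.3.1 (repeated in Appendix D) gives "PFS: disease progression or death from MDS". The same table adds "Cause-specific death: death related to MDS". Section 8.4 waives expedited reporting of progression deaths because "death due to disease progression is part of the study objectives (PFS), and captured as an endpoint in this study".

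Section 6.3.1 also defines stable disease as a state short of partial remission with no evidence of progression. Under 3.1 and 3.7.1, participants without at least a partial remission after cycle 6 stop treatment. They are then followed for up to 8 years or until death.

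**The concern.** The cause field records whether the participant was in remission, which is a different question from what caused the death. The two answers come apart for someone who is neither in remission nor progressing. The trial enrols people whose disease responded inadequately to an HMA, and its design response rates are 25% and 45% (section 10.2). Many participants may therefore never reach remission and may be followed for a long time outside it.

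At stake is the content of two endpoints. If PFS or cause-specific death is taken from this field, an unrelated death in stable disease becomes an MDS death, and the form holds nothing that would reveal the error. The plan's own background gives reason to expect some such deaths: section 1.2.1 says that "the remaining 1/3 may die from causes unrelated to their MDS".

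**Working it through.** The plan states no PFS event count, precision or power, so there is no figure to reproduce. The check is one of logic, followed by simple arithmetic for scale.

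**1. What the field forces.** With two options, and the second defined as death in clinical remission, every death outside remission falls into the first.

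| State at death | True cause | Code under Appendix I | Primary cause requested? | Death from MDS? |
|---|---|---|---|---|
| Stable disease | Unrelated | Progression/relapse | No | No, but coded as disease |
| Stable disease | MDS complication | Progression/relapse | No | Yes |
| Remission | Unrelated | Non-relapse | Yes | No |
| Remission | MDS complication | Non-relapse | Yes | Yes, recoverable from the cause item |
| After documented progression | Any | Progression/relapse, unless back in remission | Only if in remission | PFS already has its event; cause-specific death is still affected |

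Rows 1 and 2 get the same code and no further information, so they cannot be separated. A smaller point is that clinical remission is not defined here. It could mean CR only, or include PR or marrow CR, while the neighbouring status field uses CR or not CR.

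**2. Which deaths can be corrected from elsewhere.**

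- Within 30 days of last dose, all AEs are documented (6.1). A death is an SAE (8.1.2), assessed for relationship and alternate etiology and entered in the clinical database (8.2). These can be corrected.
- Beyond 30 days, serious events related to the investigational agent are still recorded (6.1). These can be corrected.
- Beyond 30 days and unrelated: no AE record is required. Follow-up items in Appendix I are vital status, AEs, MDS progression and secondary AML, with no cause of death. Follow-up is by phone, and outside records are requested at the first contact, later only if clinically indicated (3.4.1). The documents name no other source.

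**3. Scale for PFS.** Let D be deaths outside remission with no earlier documented progression, and u the share of these not due to MDS. Before any correction from AE/SAE records:

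false PFS events = D × u

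The documents give neither D nor u for higher-risk MDS. For all MDS they give about 1/3 (1.2.1) and, from 1.2.3.5, 29 unrelated deaths against 67 MDS- or treatment-related: 29 / (67 + 29) = 30.2%.

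| D | u = 10% | u = 20% | u = 30.2% | u = 1/3 |
|---|---|---|---|---|
| 10 | 1.0 | 2.0 | 3.0 | 3.3 |
| 20 | 2.0 | 4.0 | 6.0 | 6.7 |

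**4. Effect on the median.** Suppose constant hazards, with false events otherwise censored at death. If a share f of counted PFS events is false, the event rate is multiplied by 1/(1 − f) and the median by (1 − f). For f = 5%, 10% and 20% the median is multiplied by 0.95, 0.90 and 0.80. These values of f are illustrative.

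**The case against.** The strongest reply is that nothing in the plan derives PFS from this field. Appendix I is headed as data elements to consider for the CRF, so the final form may differ. This stands. A reader might infer that PFS will be wrong; the documents support only that it would be wrong if this field were its source.

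A reader might also infer that treatment-related deaths will be hidden. The documents do not support that, because the AE and SAE provisions in 6.1, 8.1.2 and 8.2 record them with attribution, including late serious events related to the investigational agent. Section 8.4 also keeps expedited reporting where a causal link to study drug is suspected.

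A third tempting step is to multiply out the non-responders. At response rates of 45% and 25%, 0.55 × 43 = 23.7 and 0.75 × 43 = 32.3 participants do not respond, and one third of these is about 8 to 11. That is not an estimate of false PFS events. It assumes every non-responder dies during follow-up and ignores earlier progression, after which death no longer alters PFS. Progression in 6.3.1 is broad: blast increase, a fall in counts or hemoglobin, or transfusion dependence. It also applies an all-MDS fraction to higher-risk disease. In the HMA-refractory patients cited in 1.2.3.2, overall survival was 9.9 months, which leaves less time for unrelated deaths.

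Finally, PFS is exploratory (1.1.3, 10.1) and its analysis descriptive (10.4.9). EFS, defined in 6.3.1 as failure or death from any cause, already gives a measure that needs no attribution. This limits the importance of the point. It leaves the classification rule itself unanswered, because the rule as written gives the wrong code for a foreseeable kind of death.

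**Conclusion.** The point holds in a limited form. As written, the field codes any death outside remission without progression as a disease death, whatever its cause, and asks for no cause. PFS and cause-specific death would be miscounted if derived from it. The gap that other records do not fill is mainly unrelated deaths outside remission more than 30 days after last dose.

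For PFS the size is about 1.0 to 3.3 false events per 10 deaths outside remission without earlier documented progression. This rests on an assumed non-MDS share of 10% to 33%, whose upper end comes from all-MDS figures and is probably high for this population. The number of such deaths is not given in the documents, so no total for the trial can be stated.

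The RP2D, the primary ORR and its two-stage decision, OS, LFS and EFS do not depend on this field. The change is worth making because it is cheap now, and a cause not recorded at the time of death may be hard to recover later.

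**What to change.** In Appendix I, under data collected at death:

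- Record the primary cause of death, with its CTCAE term where one applies, for every participant whatever the remission status.
- Add an attribution item: MDS/AML or its complications, study treatment, or unrelated.
- Keep disease status at death as a separate field.
- Derive death from MDS, for both PFS and cause-specific death, from the cause and attribution items, and say so beside the endpoint definitions.

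An additional PFS counting death from any cause is optional, since EFS largely covers it.

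The cost is one CRF field change and slightly more data entry per death. No visit, procedure or sample is added, and the sample size is unchanged.

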## **17.10 APPENDIX J: BLOOD PROCESSING CORE PROCEDURES**

Note: The following processing details and supplies may be adjusted as required during the course of the study with approval of the laboratory(ies).

### **Samples to be Collected:**

1. Peripheral Blood:
  - a. 2 x 5 mL EDTA tubes (for separation and storage of MNC and plasma, protocol below)
  - b. 4 mL SST (or 2 x 2.5ml) Vacutainer tube (for PK analysis)
  - c. 1 x 2.5ml Paxgene RNA tube (for storage then pickup by [name] lab)
2. Bone Marrow Aspirate: 2 x 5mL EDTA tubes (for separation and storage of MNC and plasma, protocol below)

